### **9.1.1. Overall Summary of Treatment Emergent Adverse Events**

An overall summary of TEAEs will be presented in a table and will include the number and percentage of patients with any TEAE, number of TEAEs, patients with serious TEAEs, TEAEs leading to death and patients that discontinued from study treatment and/or study due to TEAEs. In addition, the table will include number and percentage of patients in each category of severity (i.e. Grade 1 to Grade 5) for all TEAEs and for related TEAEs, and number and percentage of patients in each category of relationship to study drug (i.e. “Related” and “Not Related”).

### **9.1.2. Treatment Emergent Adverse Events Summary by SOC and PT**

Summaries of the total number of TEAEs and the number and percentage of patients with at least one TEAE will be provided. TEAEs will be presented by SOC and PT. At each level of patient summarization, a patient is counted once if the patient reported one or more events. Percentages will be calculated out of the number of patients in the Safety population.

The summary of TEAEs will be presented in descending order from the SOC with the highest total incidence (that is, summed across all treatment groups) to the SOC with the lowest total incidence. If the total incidence for any two or more SOCs is equal, the SOCs will be presented in alphabetical order. Within each SOC, the PTs will be presented in alphabetical order.

All TEAEs will be presented in a listing.

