## SYNOPSIS

Name of Active Ingredient:	APD334
Study Title:	An Extension Study of APD334-003 in Patients with Moderately to Severely Active Ulcerative Colitis
Study Number:	APD334-005
Indication:	Ulcerative Colitis
Study Phase	2
Sponsor:	Arena Pharmaceuticals, Inc. [name]
Name of Sponsor Contact:	[REDACTED], Research and Development & CMO Arena Pharmaceuticals, Inc [name] Phone [REDACTED]
Name of Principal Investigator(s):	Multi-center
Medical Monitor:	[REDACTED], MD [REDACTED], Clinical Development Arena Pharmaceuticals, Inc. Phone: [REDACTED] Mobile: [REDACTED]
Objectives:	Primary: To evaluate the long-term safety and tolerability of APD334 in patients with ulcerative colitis who have completed the APD334-003 study. Secondary: To evaluate the effect of APD334 on achieving and maintaining clinical response and/or remission in patients with ulcerative colitis after 46 weeks of treatment. Exploratory: [REDACTED]

	
--	--

Study Design:
	
This protocol has been designed as an open-label extension study to help determine the long-term safety and tolerability of APD334 in patients with ulcerative colitis who have completed the 12-week phase 2 study, APD334-003. To be eligible, patients must have completed the APD334-003 study and must meet eligibility criteria for APD334-005 at time of entry.
 
All patients who have completed the APD334-003 induction study and who meet the eligibility criteria for the APD334-005 extension study will have the option to enroll and receive open-label 2 mg q.d. treatment with APD334. For this purpose, all patients shall be consented for APD334-005 prior to the final procedures being performed for APD334-003.
 
Selected procedures from the Week 12 visit in study APD334-003 will be carried over to the APD334-005 study to be included as baseline information for certain analyses. 
 
Following the Day 1 visit, there will be regular visits to monitor for safety and perform efficacy assessments throughout the treatment period. Final efficacy assessments will be conducted at

-----------------------------	---

[figure not shown]

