## PROTOCOL AMENDMENT SUMMARY

The following is a list of **major** changes made to the APD334-005 Protocol dated 28 September 2015. Minor clarifications and corrections have been made throughout for consistency. These changes are incorporated in Protocol Amendment 03 dated 20 October 2016.

Section(s) Amended	Page No(s).	Description of Changes Made
Header/Footer, Title Page, and TOC	All	Added "Amendment 03", updated date to reflect finalization of amended protocol, updated pagination and TOC.
Protocol Amendment Summary	2-5	Updated table to include summary of changes to the protocol.
Synopsis	6	Updated sponsor contact and medical monitor.
Synopsis	7-8	Changed study duration from 52 weeks to 46 weeks total (including the APD334-003 study).
Synopsis	7-8	Changed study design to open label (2 mg) for APD334-003 responders only.
Synopsis	7-8	[REDACTED]
Synopsis	8-9	Updated secondary and exploratory outcome measures to reflect study duration of 46 weeks total (including the APD334-003 study).
Synopsis	9-10	[REDACTED]
Synopsis	10	Updated data analyses section to reflect changes in study design.
Synopsis	11	Updated figure "Study Design" according to the changes.
Study Definitions	20	Removed definitions of initial and new Day -1 or Day 1 to reflect amended study design (responders only).
2.2 Secondary Objective	27	Updated to "46 weeks of treatment"
3.1 Overall Study Design and Plan	28	Updated to reflect changes to single arm, open-label, 2 mg q.d. for responders in APD334-003 only.

3.1 Overall Study Design and Plan	28	[REDACTED]
3.2 Study Duration and Dates	28	Changed study duration from approximately 42 weeks to up to 36 weeks.
4.2 Inclusion Criteria 6	29-30	Changed “completion of the study as planned” to “completion of the study as responder”. Added definition of “responder”.
5.1.2 Placebo	31	Changed to “Not applicable”.
5.3 Selection and Timing of Dose for Each Patient	31	Updated to reflect eligibility for responders only.
5.4 Method of Assigning Patients to Treatment Groups	31-32	Updated to reflect changes to single arm, open-label, 2 mg q.d. for responders in APD334-003 only.
5.5.1 Randomization	32	Changed to “Not applicable”.
5.5.2 Blinding	32	Updated to reflect change to open-label.
5.5.3 Maintenance of APD334-003 Randomization Codes and Code-break Procedures	32	Changed to “Not applicable”.
5.6 Concomitant Therapy	32	[REDACTED]
5.11 Data Safety Monitoring Board	33	Changed to “Not applicable”.
6.5 Vital Signs	35	[REDACTED]
[REDACTED]	35	[REDACTED]

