### 3. INVESTIGATIONAL PLAN

#### 3.1. Overall Study Design and Plan

APD334-005 is a phase 2, open-label extension study to determine the long-term safety and tolerability of etrasimod as well as its ability to achieve and maintain clinical remission and response after 34 weeks of additional treatment in patients with ulcerative colitis who have completed the APD334-003 induction study.

Eligible patients must have completed the APD334-003 induction study and must meet the eligibility criteria for the APD334-005 at time of entry. All eligible patients will have the option to enroll and receive open-label 2 mg q.d. treatment with etrasimod. For this purpose, all patients shall be consented for APD334-005 prior to the final procedures being performed for APD334-003 (as some procedure results will be used for the extension study baseline).

Selected procedures from the Week 12 visit in study APD334-003 will be carried over to the APD334-005 study to be included as baseline information and assist in determining eligibility for the APD334-005 study. [REDACTED]

[REDACTED]. Following the Day 1 visit, there will be regular visits to monitor for safety and perform efficacy assessments throughout the treatment period. Final assessments will be conducted at Week 46 from Baseline of study APD334-003 (Week 34 of this study), or upon early termination from the study. A 2-week follow-up visit will be conducted to ensure appropriate patient safety [REDACTED]

The total study participation/duration is up to 36 weeks (34 weeks of treatment and a 2-week follow-up visit after final visit). The schedule of procedures and visits for the study is provided in [Appendix 14.1](#).

[REDACTED] Patients who terminate early or discontinue from the study will not be replaced.

Note: Patients that were enrolled under Protocol Amendment 02 (28 Sep 2015) followed a different study design (i.e. patients were randomized to Placebo or 2 mg q.d. etrasimod and remained blinded, and final assessments were conducted at Week 52 instead of Week 46). More details about changes in the study design are covered in Sections [1](#) and [12](#).

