## 9. SAFETY ANALYSIS

The safety of etrasimod will be monitored throughout the study with safety endpoints being as follows:

- Treatment-emergent adverse events (TEAEs) up to 30 days following discontinuation of the study drug
- Treatment-emergent serious adverse events (SAEs) up to 30 days following discontinuation of the study drug

Additional safety assessments will include:

- Physical & neurological examinations including ophthalmoscopy (and optical coherence tomography [OCT], where available)
- Progressive multifocal leukoencephalopathy (PML) checklist
- Clinical laboratory tests to include hematology, serum chemistry, coagulation, and urinalysis
- Vital sign measurements
- Pulmonary Function Tests (PFTs)
- ECGs
- AE reporting

For analyses based on laboratory measurements, vital signs and ECGs, summary tabulations (n, mean, SD, median, minimum and maximum for actual and change [or percent change] from baseline) will be presented. For analyses based on AEs, frequency and percentage will be presented. The analyses for all safety outcomes (categorical or continuous measures) will use the Safety population.

For analysis based on laboratory measurements, at least 1 laboratory test post-enrollment measurement in the extension study is required for inclusion in the Safety population. When assessing change from baseline, a baseline measurement is also required. Baseline for the safety analysis is defined as the last pre-enrollment measurement (i.e. APD334-005 Day 1 pre-dose). No missing data will be imputed for the safety analysis.

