- TEAEs that leading to permanent discontinuation of study drug by SOC and PT
- TEAEs with severity grade  $\geq 3$  by SOC and PT

Patients will be monitored from Informed Consent Form (ICF) signature to 30 days after the last dose of study drug for adverse reactions to the study drug and/or procedures.

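### A cheap improvement: add patient-year rates to the TEAE tables, because planned treatment was 40 or 34 weeks by amendment and early stoppers count in full

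*SAP*

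**What the plan says.** - **Measure.** SAP Section 9 sets the general rule: "For analyses based on AEs, frequency and percentage will be presented". Section 9.1.2 adds event totals: "Summaries of the total number of TEAEs and the number and percentage of patients with at least one TEAE will be provided".
- **Denominator.** Section 9.1.2: "Percentages will be calculated out of the number of patients in the Safety population". Sections 9.1.3 to 9.1.6 also use the Safety population. Section 4.4.3 puts every patient who received extension medication in it, so a patient who stops early counts the same as one who completes.
- **Planned duration.** Under the current design, treatment ends at Week 46 counted from APD334-003 baseline, which is Week 34 of the extension. For patients enrolled under Amendment 02, SAP Section 3.1 says "final assessments were conducted at Week 52 instead of Week 46".
- **Columns.** SAP Section 12 pools 2 mg patients from all amendments. The Placebo group holds only patients from before Amendment 03. SAP Section 4 lays out six columns side by side and states that there is no formal between-group comparison.
- **Exposure.** Section 7.2.2 summarises duration of exposure, from first to last dose, for the Safety population. Nothing in the readable text of Section 9.1 uses it: there is no patient-time rate and no time-to-first-event analysis.
- **TEAE definition.** Section 9.1 also counts as TEAEs events that began in APD334-003 and are ongoing, or end, in the extension.

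**The concern.** The proportion of patients with at least one event depends on how long they are watched. Here the planned watching time differs by amendment, the Placebo column is entirely on the longer plan, and the 2 mg column is a mixture. Patients who stop early shorten the average time at risk further without leaving the denominator. A difference between the Placebo and 2 mg columns can therefore reflect time at risk as well as treatment. Even within one column, the percentage does not describe a defined length of exposure, which is what a reader of a long-term safety study wants to know. The dates needed for a time denominator are already collected.

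**Working it through.** **Inputs from the documents**

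| Input | Value | Source |
|---|---|---|
| Length of induction | 12 weeks ("completed the 12-week phase 2 study, APD334-003") | Protocol Synopsis |
| End of treatment, current design | Week 46 | SAP 3.1 |
| End of treatment, Amendment 02 | Week 52 | SAP 3.1 |
| Follow-up visit | 2 weeks after final visit | SAP 3.1 |
| AE collection | "signature to 30 days after the last dose of study drug" | SAP 9.1 |

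**Step 1. Reproduce the plan's own durations.** 46 − 12 = 34 weeks of treatment, and 34 + 2 = 36 weeks of participation. 52 − 12 = 40 weeks, and 40 + 2 = 42. Both agree with the Amendment 03 change log: "Changed study duration from approximately 42 weeks to up to 36 weeks".

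**Step 2. Planned time at risk.** 34 × 7 + 30 = 268 days. 40 × 7 + 30 = 310 days. The ratio is r = 310/268 = 1.157 (for treatment time alone, 40/34 = 1.176).

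**Step 3. Effect on a crude percentage.** Assume the same constant hazard in both groups and no early stopping. If a proportion p has an event in 268 days, then 1 − (1 − p)^r has one in 310 days. The values of p are assumptions.

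| 34-week plan | 40-week plan | Gap (points) |
|---|---|---|
| 1% | 1.2% | 0.2 |
| 10% | 11.5% | 1.5 |
| 30% | 33.8% | 3.8 |
| 50% | 55.1% | 5.1 |
| 60% | 65.4% | 5.4 |
| 80% | 84.5% | 4.5 |

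The gap peaks at about 5.4 points, near 60%. For rare events it is about 16% in relative terms.

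**Step 4. The 2 mg column is mixed.** The documents do not give the mix. With an assumed 50:50 split, the gap at 50% halves: (55.15 − 50.00)/2 = 2.6 points.

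**Step 5. Early stopping.** Assume a fraction d stops uniformly over the planned treatment, unrelated to AEs, each followed for 30 more days. Mean time at risk on the 34-week plan is (1 − d) × 268 + d × (119 + 30). On the 40-week plan it is (1 − d) × 310 + d × (140 + 30). With d = 0.40 these give 220 and 254 days. An incidence that would be 50% over the full 268 days then reads 45.2% with d = 0.25 and 42.4% with d = 0.40. A 40-week group with d = 0.40 has 254 days, below the 268 days of a 34-week group with no stopping. At equal hazard it would show 46.8% against 50.0%, so the gap can reverse.

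**Step 6. Carried-over events.** A patient who brings an ongoing event from APD334-003 counts as having a TEAE from day 0, whatever the follow-up. If, as an assumption, 20% do so and 50% have any TEAE at 34 weeks, the 40-week figure is 1 − 0.80 × (0.50/0.80)^1.157 = 53.6%, not 55.1%. This reduces the dependence on follow-up for the any-TEAE row. It also means that a first-event rate needs a rule for such patients, who have no time at risk before their event.

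**The case against.** The strongest reply is that the plan is descriptive and already supplies much of what is needed. That is largely fair.

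- A reader might infer that safety is reported only as crude percentages. It is not: event totals are planned in the same tables, and exposure is summarised for the same population. An approximate rate of events per patient-time can be worked out from those outputs. What cannot be worked out is a first-event incidence rate. Exposure in Section 7.2.2 also stops at the last dose, whereas AEs are collected for 30 more days.
- A reader might infer that none of the columns can be compared. The documents show a difference in planned length only for Placebo against 2 mg. They do not give the 34/40-week mix in the columns by prior APD334-003 treatment, so a difference there is possible but not shown.
- The plan disclaims formal comparison between groups, and the readable text plans no AE comparison with the 12-week APD334-003 rates. No test or decision depends on the gap.
- Placebo against 2 mg is confounded by selection in any case. SAP Section 12 says that under Amendment 02 Placebo went only to APD334-003 responders, while non-responders received open-label 2 mg. A time denominator does not change that.
- A reader might infer that high dropout makes the drug look safer. Step 5 shows this only for stopping unrelated to AEs. A patient who stops because of an AE already counts as an event, and Section 9.1.6 tabulates these cases.

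What remains is that the columns will be printed side by side, and each percentage covers an unstated mixture of follow-up times. That applies to the single-arm description too, so the absence of formal testing does not remove it.

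**Conclusion.** The point holds as a low-cost improvement, not as an error that invalidates the safety tables. The primary endpoint has no time-at-risk denominator, although planned treatment was 40 or 34 weeks by amendment and everyone dosed counts in full. Planned length alone moves a crude percentage by at most about 5.4 points between pure groups, and by about 2.6 points at 50% incidence if the 2 mg column is an even mix. Early stopping can be as large an influence and can act in either direction between columns, so a reader cannot correct the percentages by eye. These sizes rest on a constant hazard and on assumed incidences, mix and dropout. Carried-over events make the any-TEAE effect smaller than modelled.

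**What to change.** In SAP Section 9.1, keep event totals and n (%), and add an exposure-adjusted incidence rate with a CI for each Section 4 column.

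- **Categories:** any TEAE, serious TEAEs, TEAEs of grade 3 or higher, and TEAEs leading to discontinuation.
- **Numerator:** patients with a first event in the category that is new in onset, or has worsened, in APD334-005.
- **Denominator:** time from first extension dose to that first event or, without one, to the end of AE follow-up, at most 30 days after the last dose. Express the rate per 100 patient-years.
- **Carried-over events:** leave events that continue unchanged from APD334-003 out of the numerator and report them on a separate row. State how events with a wholly missing onset date are handled.
- **Interpretation:** add a sentence that the rates are descriptive, assume a constant rate, and do not remove the responder selection into Amendment 02 Placebo.

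The cost is four categories in six columns, 4 × 6 = 24 rates with CIs, from dates already collected. Extending the rates to every SOC and PT row is not needed: many rows are likely to be sparse in a study limited to APD334-003 completers.

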### **9.1.3. Relationship of Adverse Events to Study Drug**

A summary of total number of TEAEs and number and percentage of patients with at least one TEAE by relationship (i.e. “Related” and “Not Related”) to study drug will be presented in a table by incidence of occurrence.

The investigator will provide an assessment of the relationship of the event to the study drug. The possible relationships are “Not Related” or “Related”. In the TEAE relationship table, if a patient reports multiple occurrences of the same TEAE, only the most closely related occurrence will be presented. Percentages will be calculated out of the number of patients in the Safety population.

The TEAE data will be categorized and presented by SOC, PT, and relationship.

### **9.1.4. Severity of Adverse Events**

A summary of total number of TEAEs and number and percentage of patients with at least one TEAE by severity will be presented in a table.

The severity that will be presented represents the most extreme severity captured on the CRF page. The possible severities are Grade 1 to Grade 5 i.e. “Mild” “Moderate”, “Severe”, “Life-threatening” and “Death related”, respectively. In the TEAE severity table, if a patient reported multiple occurrences of the same TEAE, only the most severe will be presented. Percentages will be calculated out of the number of patients in the Safety population.

The TEAE data will be categorized and presented by SOC, PT, and severity.

In addition, a similar table will be produced for TEAEs that have severity of Grade  $\geq 3$ .

### **9.1.5. Serious Adverse Events**

The seriousness of an AE should be assessed by the Investigator independently from the severity of the AE. A SAE is defined as any untoward medical occurrence that at any dose results in death, is life-threatening, is a congenital anomaly/birth defect, requires in-patient hospitalization or prolongation, or results in significant disability/incapacity.

Important medical events that may not result in death, be life-threatening, or require hospitalization may be considered SAEs when, based upon medical judgment, they may jeopardize the patient and may require medical or surgical intervention to prevent one of the outcomes listed above.

Summaries of the total number of SAEs and the number and percentage of patients with at least one SAE will be provided. SAEs will be presented by SOC and PT. At each level of patient summarization, a patient is counted once if the patient reported one or more events. Percentages will be calculated out of the number of patient in the Safety population.

The summary of SAEs will be presented in descending order from the SOC with the highest total incidence (that is, summed across all treatment groups) to the SOC with the lowest total incidence. If the total incidence for any two or more SOCs is equal, the SOCs will be presented in alphabetical order. Within each SOC, the PTs will be presented in alphabetical order.

All SAEs will be presented in a listing by patient using the Safety population. If there are no SAEs at the end of the study, the tables or listings will state that there are no SAEs in the study.

### **9.1.6. Adverse Events Leading to Study Discontinuation**

A summary of total number of TEAEs and number and percentage of patients with at least one TEAE that caused permanent discontinuation of study medication (i.e. study medication discontinued and/or withdrawal from study) will be presented. TEAEs will be presented by SOC and PT. At each level of patient summarization, a patient is counted once if the patient reported one or more events. Percentages will be calculated out of the number of patients in the Safety population within the subgroup category.

The summary of TEAEs that caused permanent discontinuation of study medication will also be presented in descending order of frequency from the SOC with the highest total incidence (that is, summed across all treatment groups) to the SOC with the lowest total incidence. If the total incidence for any two or more SOCs is equal, the SOCs will be presented in alphabetical order. Within each SOC, the PTs will be presented in alphabetical order.

## **9.2. Clinical Laboratory Evaluations**

Clinical laboratory evaluations (i.e. hematology, serum chemistry, coagulation and urinalysis) will be performed by a central laboratory. All summaries will be based on the units provided by the central laboratory, no conversion will be performed.

Summary tabulations (i.e. n, mean, SD, median, minimum and maximum) for the observed values and changes from baseline will be presented for clinical laboratory evaluations with numeric values for patients in the Safety population. Observed results at each visit and changes from baselines (APD334-003 baseline and APD334-005 baseline) to each scheduled post-baseline visit will be presented.

All relevant clinical laboratory tests will be classified as Low, Normal, and High according to the normal ranges. This categorical data will be summarized in shift tables comparing the results at last scheduled post-baseline visit with those at the baseline visit. Baseline for APD334-003 study is defined as last measurement before first dose of study medication in APD334-003 study, and baseline for APD334-005 study is defined as last pre-enrollment measurement (APD334-005 Day 1 pre-dose).

If any laboratory value falls above or below the upper or lower level of quantification, the value of the upper or lower level of quantification will be taken (e.g.  $<0.2$  will become 0.2) for summaries but left as recorded in the listing.

All individual lab values will be listed by visit.

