#### 3.2 Study Duration and Dates

The total study participation/duration is up to 36 weeks (34 weeks of treatment and a 2-week follow-up visit after final visit). The schedule of procedures and visits for the study are provided in Appendix 1.

---

[figure not shown]

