### 6.10.2 Hematologic Sampling

Blood samples for CBC with differential and platelet count will be assessed [REDACTED].

If the [REDACTED] value at the 2-week follow-up, patients should return for weekly CBCs until the absolute peripheral lymphocyte count has returned to at least this value.

All details regarding collection of blood samples for CBC with differential analysis will be collected and prepared according to that specified in the laboratory manual provided separately by the central laboratory. The samples should be packed and shipped to the central laboratory, according to the directions in their laboratory manual, which will send them on to the bioanalytical laboratory for analysis.

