#### 7.2.2.5 2-week Follow-up Procedures, End of Study (EoS)

A 2-week follow-up visit to include additional safety assessments will be completed for all patients as outlined in the schedule of procedures and visits (Appendix 1). Patients will not receive study medication during the follow-up period.

---

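### The laboratory shift tables in SAP 9.2 rest on one end visit with no on-treatment limit, so abnormalities that resolve before that visit do not appear in them

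*SAP*

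**What the plan says.** SAP 9.2 covers hematology, serum chemistry, coagulation and urinalysis. For the categorical summary it states: "This categorical data will be summarized in shift tables comparing the results at last scheduled post-baseline visit with those at the baseline visit". The end point is one visit per patient. The visible text does not tie it to dosing.

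The same section reports continuous data more fully: "Observed results at each visit and changes from baselines (APD334-003 baseline and APD334-005 baseline) to each scheduled post-baseline visit will be presented". It defines both baselines immediately after the shift-table sentence but does not say which one the shift tables use. The parent section, SAP 9, has a general rule: "Baseline for the safety analysis is defined as the last pre-enrollment measurement (i.e. APD334-005 Day 1 pre-dose").

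Two sets of passages bear on which visit comes last:

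- Protocol 3.2 describes participation as "34 weeks of treatment and a 2-week follow-up visit after final visit", and SAP 3.1 says: "Final assessments will be conducted at Week 46 from Baseline of study APD334-003 (Week 34 of this study), or upon early termination".
- Protocol 7.2.2.5, whose heading calls the visit End of Study, says: "A 2-week follow-up visit to include additional safety assessments will be completed for all patients". It adds: "Patients will not receive study medication during the follow-up period". Protocol 6.10.2 acts on a blood count at that visit; part of the sentence is redacted, but it continues: "value at the 2-week follow-up, patients should return for weekly CBCs until the absolute peripheral lymphocyte count has returned".

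Protocol 9.8.5 ends the same shift tables at the last visit under double-blind treatment. That does not fit the current open-label design. The visible part of SAP 12 does not record the change of end point.

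**The concern.** The primary objective is long-term safety, and lymphocyte lowering is the drug's stated mechanism. The shift table is the only categorical laboratory summary visible in SAP 9.2, so it is where a reader would look to see how many patients moved from Normal to Low or High. Means and medians by visit do not give that count.

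A table that compares baseline with one end visit counts only abnormalities present at that visit. A patient who was Low for part of the treatment period and Normal at the end appears as Normal to Normal. If the end visit falls off drug, patients who recover after stopping are missed as well. The word scheduled can also be read as leaving out the extra samples that Protocol 6.11.8 allows when a clinically important adverse event occurs.

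**Working it through.** The documents give no figure for this table, so there is nothing to reproduce. The check is a comparison of passages, a timing calculation and a labelled illustration.

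**Step 1. Which visit is last?**

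- *Week 46/end of treatment (EOT).* Protocol 3.2 places the follow-up after the final visit, and SAP 3.1 places final assessments at Week 46 or early termination. Protocol 7.2.2.4 lists the full laboratory panel there.
- *The 2-week follow-up.* Protocol 7.2.2.5 plans it for all patients under the visit schedule and after baseline, so in plain words it is a scheduled post-baseline visit. Protocol 6.10.2 implies a blood count there, and Protocol 6.8.1 lists the white cell count with differential under hematology, which SAP 9.2 covers.

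The visit schedule (Protocol Appendix 1, SAP 14.1) and the day ranges of SAP 4.1 are not visible in the public file, so neither reading can be confirmed. The text supports the second reading for blood counts only. Nothing visible places chemistry, coagulation or urinalysis at the follow-up visit.

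**Step 2. How far apart are the readings?** For the Week 46 design:

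- 12 weeks in APD334-003 + 34 weeks here = Week 46.
- EOT: 34 × 7 = day 238 of this study.
- Follow-up: 34 + 2 = 36 weeks, which matches the stated maximum participation; 36 × 7 = day 252.
- Difference: 252 − 238 = 14 days without drug.

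Patients enrolled under Amendment 02 had final assessments at Week 52, so these day counts do not apply to them.

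**Step 3. What could the table miss?** All inputs here are assumptions. Per 100 patients, let 30 be Low at some on-treatment visit. Let s be the share of those still Low at EOT, and r the share of these back to Normal by follow-up. Assume that no patient who is Normal at EOT becomes Low by follow-up.

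- Worst on-treatment table: 30
- End visit at EOT: 30 × s
- End visit at follow-up: 30 × s × (1 − r)

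| s | Worst on-treatment | EOT | Follow-up, r = 0 | Follow-up, r = 50% | Follow-up, r = 90% |
|---|---|---|---|---|---|
| 100% | 30 | 30 | 30 | 15 | 3 |
| 80% | 30 | 24 | 24 | 12 | 2.4 |
| 50% | 30 | 15 | 15 | 7.5 | 1.5 |

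At s = 100% and r = 0 nothing is lost. The EOT column shows that the single-visit design can miss cases even if the end visit is on drug; the follow-up columns show a possible further loss. The weekly counts required by Protocol 6.10.2, and the five patients in SAP 12 whose blood counts were followed after last treatment, suggest that r is below 100%. They do not give its value.

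**The case against.** The strongest case against the point is that on-treatment data are already reported. SAP 9.2 gives summaries with minimum and maximum at each visit, changes from both baselines and a listing of every individual value. SAP 9.6 tabulates lymphocytes by visit. SAP 9.1 tabulates adverse events by grade, and Protocol 6.11.1 counts an abnormal laboratory finding as a possible adverse event. The primary endpoints are treatment-emergent adverse events and serious adverse events; SAP 9 lists laboratory tests as additional assessments. A shift from baseline to a last visit is a common summary, and neither document promises a worst-value table.

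Most of this stands and sets the size of the point. Two parts do not remove it. By-visit summaries do not count patients who crossed a reference limit at any time. For white cells and lymphocytes the adverse event route is also thinner than usual: Protocol 9.8.5 leaves recording to the investigator or sponsor, while Protocol 5.5.2 blinds the sponsor and study personnel to these counts and has an unblinded central physician review them.

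A reader might infer that the shift tables do end off drug. The documents do not support that. Protocol 3.2 and SAP 3.1 favour EOT, and the schedule and table shells that could settle the matter are not in the public file. A reader might also infer that the baseline is undefined. SAP 9 supplies a default, so the open question is only whether the shift tables follow it or use both baselines, as the by-visit changes do.

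**Conclusion.** The point holds as a minor improvement to the safety description. SAP 9.2 bases its only visible categorical laboratory summary on one end visit with no on-treatment limit, and such a table misses on-treatment abnormalities that resolve before that visit. That follows under either reading of the end visit. The off-drug reading is possible for blood counts on the literal wording, but it is unconfirmed and cannot be extended to other tests.

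The size cannot be derived from the documents. The illustration runs from no loss to nearly all cases missed, depending wholly on assumed inputs, and should not be read as an estimate. No hypothesis test or primary endpoint is affected. Naming the baseline and logging the changed end point are clarifications that would not justify a point on their own.

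**What to change.** In SAP 9.2:

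1. Define shifts from baseline to the worst on-treatment low, the worst on-treatment high and the last on-treatment value. Set on-treatment by sample date relative to the first and last APD334-005 dose. This also handles early termination and the different Amendment 02 schedule.
2. Include unscheduled central-laboratory samples in the worst-value shifts. Restricting these to the central laboratory fits the section's rule that summaries use its units without conversion.
3. Show the 2-week follow-up separately as recovery.

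As housekeeping, state that the shift tables use both the APD334-003 and APD334-005 baselines, shown in the prior-treatment columns of SAP 4. For patients previously on 1 mg or 2 mg, the APD334-005 baseline follows 12 weeks of active treatment, so a drop during APD334-003 would otherwise appear as Low to Low. Record in SAP 12 the change from the end point in Protocol 9.8.5.

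The cost is SAP wording and a few more tables to produce and review, from data already collected. If the database is already locked, Protocol 9 and SAP 1 provide for describing the change and its reason in the clinical study report.
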